Post Tetanic Count (PTC). In contrast to TOF stimulation, PTC can be used to determine the degree of neuromuscular blockade under conditions of a deep neuromuscular block. A 50 Hz stimulus, given for 5 seconds, is applied at the skin over the ulnar nerve. Three seconds after this stimulus, muscle contraction is counted in response to single 1 Hz stimulation. In an intense neuromuscular block, no PTC response may be observed.

Acceleromyography (AMG): method to measure neuromuscular transmission. A piezoelectric device measures thumb acceleration after stimulation of the ulnar nerve

Electromyography (EMG): Gold standard to measure neuromuscular transmission. Evoked action potentials after stimulation of a peripheral nerve are recorded in a muscle innervated by that nerve. Usually

Abstract

Introduction

Neuromuscular monitoring is mandatory during anesthesia. Acceleromyography (AMG) is the most wide spread used method because it is easy to apply and accurate enough for daily practice. However AMG is known to be inaccurate when compared to the gold standard in neuromuscular transmission monitoring, electromyography (EMG). Furthermore when the patients arms require to be positioned next to the body and beneath surgical drapes, AMG measurements are often hindered and inaccurate. The TOF cuff is a new device which measures NMB at the upper arm with a blood pressure cuff. It overcomes the previously mentioned disadvantages of AMG. However, its validity compared to EMG has not yet fully been investigated.

Aim

To compare the bias, limits of agreement and precision of the TOF cuff relative to EMG on both the ipsi- and contralateral arm during recovery of moderate and deep neuromuscular block in patients with normal body mass index and morbidly obese patients.

Methods

This is an observational, non-inferiority trial in which we will compare the TOF cuff device to electromyography (EMG). All patients will receive general total intravenous anesthesia (propofol/remifentanil/rocuronium). Patients will have the TOF cuff and EMG placed on the same extremity (hand for EMG, upper arm for TOF cuff). Measurements will be done during induction, maintenance and recovery from a moderate (GROUP 1) and deep (GROUP 2) neuromuscular block. Patients will enter the study in group 1 or 2 based on the required procedure. In other words, the procedure dictates the desired level of neuromuscular block (moderate or deep), not the study. We will perform a pilot study with 200 patients (150 patients with normal BMI ($< 30 \text{ kg/m}^2$) and 50 patients with morbid obesity ($> 35 \text{ kg/m}^2$) to ensure that reliable estimates of repeatability coefficient, bias, and limits of agreement are obtained. After 100 patients (50 non-obese/50 obese) we will perform an interim analysis and calculate the remaining number of patients needed to complete the study. The protocol was amended (19-11-2018) to include 50 extra patients to investigate relative bias between ipsi- and contralateral comparisons between TOF Cuff and EMG in patients. Total number of included patients will be 250. The interim analysis at 100 included patients showed a significant difference between the TOF Cuff and the EMG regarding the time to complete spontaneous recovery of neuromuscular block. The time to complete recovery is clinically the most relevant outcome as this reflects zero chance of residual NMB by definition. To increase the emphasis on time until full spontaneous recovery, the protocol was amended (19-6-19) to include 50 patients at the LUMC that were originally scheduled for inclusion at the Nederlandse Obesitas Kliniek (NOK). The very reason for this, is the fact that at the NOK, sugammadex reversal is routinely applied to facilitate quick changeover of patients. However, this practice interferes with the objective of

evaluating time until complete spontaneous (unreversed) recovery of the NMB. Transferal of 50 intended study subjects from the NOK to the LUMC will allow us to gather more data on the relevant final stages of the spontaneous recovery of NMB

1. Introduction

Neuromuscular monitoring is mandatory during anesthesia when using muscle relaxants. Lack of monitoring has for years been associated with increased risk of postoperative residual curarisation and pulmonary complications.(1, 2) In addition, monitoring is of utmost importance during the application of a deep neuromuscular block. Monitoring is important for optimal steering of the depth of the neuromuscular block (NMB) during surgery and reversal at the end of surgery. As such, optimal neuromuscular monitoring is of importance for various reasons (1) optimizing surgical conditions; (2) to prevent complications during surgery (e.g., sudden patient movement) and (3) to prevent postoperative complications due to incomplete recovery of the NMB. (3, 4) There are several methods to monitor a NMB; each technique has its specific advantages and disadvantages. Gold standards are electromyography (EMG) and mechanomyography (MMG). However, these methods require specific equipment. Hence, for practical reasons, acceleromyography (AMG, such as the TOF Watch) of the thumb is the most widespread neuromuscular monitor in use. This method uses a piezoelectrical detector, which measures acceleration of the thumb after ulnar nerve stimulation. Major disadvantages of AMG are that it is not very accurate, and it requires a free and unrestricted moving thumb (which may not always be available due to specific patient positioning requirements) and a thumb preload (which is often unavailable, yielding inaccurate results). In conclusion, AMG is suitable in daily practice for *most* procedures due to its ease of use. However, during prolonged procedures, or when the thumb is covered by surgical drapes, AMG monitoring is often inadequate.(5)

The TOF cuff is a new device that overcomes most of the issues associated with the use of an AMG technique. The TOF cuff measures neuromuscular transmission on the upper arm with a blood pressure cuff. Two electrodes in the cuff elicit a response in the upper arm musculature. The device records the pressure changes in the blood pressure cuff following stimulation and calculates the depth of the NMB.(6) It has the advantage of not being influenced by surgical positioning, as it does not require a free moving thumb.

We have successfully used the TOF cuff in the BLISS 2 and Neuropa studies.(7, 8) We find it to be far superior in ease of use over AMG. However, several reviewers questioned the validity of the device during the review process of both studies. A small validation study the TOF cuff has been conducted several years ago and produced acceptable bias and limits of agreement when compared to mechanomyography during recovery of a moderate neuromuscular block. However, the TOF cuff was

not assessed during deep neuromuscular block and not compared to EMG and the authors concluded that additional validation of the device is necessary.(6)

In this study we intend to further validate the TOF cuff and compare it to EMG during recovery of both moderate and deep neuromuscular block. We will study patients of normal and high body mass index values.

2. Objectives

To compare the bias, limits of agreement and precision of the TOF cuff relative to EMG during recovery of moderate and deep neuromuscular block in patients with normal body mass index and morbidly obese patients.

Hypothesis

The TOF cuff behaves similarly to EMG in terms of bias, limits of agreement and precision when comparing the TOF cuff to EMG.

3. Study design

This is an observational, non-inferiority trial in which we will compare the TOF cuff device to electromyography (EMG). We will do this in 100 patients with $BMI < 30 \text{ kg/m}^2$ and 50 patients with $BMI > 35 \text{ kg/m}^2$. The protocol was amended (19-11-2018) to include 50 extra patients to investigate relative bias between ipsi- and contralateral comparisons between TOF Cuff and EMG in patients with normal BMI. Total number of included patients will be 250. The preliminary analysis after 100 patients showed that a significant difference occurs in the comparison between the TOF Cuff and the EMG regarding the time to full recovery of neuromuscular block. The time to complete recovery is clinically the most relevant outcome. To increase emphasis on time until full recovery, the protocol was amended (19-6-19) to include 50 patients in the LUMC which were originally scheduled for the NOK. In the NOK sugammadex is routinely administrated which disables evaluation of the time until complete recovery.

All patients will receive general total intravenous anesthesia (propofol/remifentanil/rocuronium). Patients will have the TOF cuff and EMG placed on one extremity (hand for EMG, upper arm for TOF cuff).

Measurements will be done during induction, maintenance and recovery from a moderate (GROUP 1) and deep (GROUP 2) neuromuscular block. Patients will enter the study in group 1 or 2 based on the required procedure. In other words, the procedure dictates the desired level of neuromuscular block (moderate or deep) not the study. Patients will therefore enter the study in a non-randomized fashion.

In group 1, the target level of neuromuscular block is TOF 1-3 twitches (moderate neuromuscular block). Time to 90% depression of the first twitch will be recorded. Measurements will be performed during spontaneous recovery from T1 until full recovery to a TOF ratio of 1.0. After that, if time allows, a new rocuronium bolus will be given to reach a target TOF 1-3 twitches. Every 60 seconds, EMG measurements will be followed by TOF cuff.

In group 2 target depth of neuromuscular block after induction is 1 PTC (deep neuromuscular block). Time to 90% depression of the first twitch will be recorded. After that, spontaneous recovery will be allowed to a PTC of 10. After that, if time allows, a new bolus of rocuronium will be administered to again reach a PTC of 1 followed by spontaneous recovery. Again, EMG measurements will be followed by TOF cuff measurements on the other arm measurements at 5 min intervals.

[figure not shown]

Fig 1. Study outline

4. Study Population

4.1 Patients and patient requirements/procedures

A total of 200 patients (150 BMI < 30 kg/m² and 50 BMI >35 kg/m²) scheduled for general anesthesia with the use of muscle relaxants will be included in this study.

The protocol was amended (19-11-2018) to include 50 extra patients to investigate relative bias between ipsi- and contralateral comparisons between TOF Cuff and EMG in patients with normal BMI. Total number of included patients will be 250. The preliminary analysis after 100 patients showed that a significant difference occurs in the comparison between the TOF Cuff and the EMG regarding the time to full recovery of neuromuscular block. The time to complete recovery is clinically the most relevant outcome. To increase emphasis on time until full recovery, the protocol was amended (19-6-19) to include 50 patients in the LUMC which were originally scheduled for the NOK. In the NOK sugammadex is routinely administrated which disables evaluation of the time until complete recovery.

4.2 Patient inclusion criteria

- (i) ASA class I-III
- (ii) > 18 years of age;
- (iii) Ability to give oral and written informed consent.

4.3 Patient exclusion criteria

- (i) Known or suspected neuromuscular disorders impairing neuromuscular function;
- (ii) Allergies to muscle relaxants, anesthetics or narcotics;
- (iii) A (family) history of malignant hyperthermia;
- (iv) Women who are or may be pregnant or are currently breast feeding;
- (v) Renal insufficiency, as defined by a glomerular filtration rate < 30 ml/min
- (vi) Scheduled for anesthesia without the use of muscle relaxants.

5. Study procedures

Pre operative procedures. Eligible patients will be informed about the study and asked to complete the informed consent on the preoperative screening visit. This will generally be one or two weeks prior to the surgery. General preoperative examination and testing will be done as usual at the preoperative outpatient department. At all time periods prior to the induction of anesthesia the patient may withdraw from the study.

Recruitment. Subjects will be recruited after approval of the study protocol by the medical ethics committee of the LUMC. Eligible subjects will be informed and recruited at the preoperative outpatient department by an anesthesiologist.

Informed consent. Patients will receive verbal and written information about the study. A written informed consent must be completed for a subject to enter the study.

Medical examination. Full medical examination and relevant blood laboratory tests will be completed at the preoperative outpatient department.

Pre-study requirements. Pre study requirements will be no different compared to patients undergoing surgery under general anesthesia. This includes refraining from eating six hours before surgery and refraining from drinking two hours before surgery.

5.1.1 Anesthesia

Standard anesthesia monitoring will be applied (blood pressure, electrocardiography, plethysmography) and will include bispectral index (BIS module, Philips, Eindhoven, The Netherlands) to assess the level of hypnosis. Intravenous access will be obtained in the antecubital fossa on the EMG arm such that it doesn't hinder EMG measurements. Central body temperature will be measured at the nasopharynx and maintained at 35.5-37.5 degrees Celsius. Peripheral (skin) temperature measured on the palms of the hands on which neuromuscular monitoring is applied will be maintained at >32 degrees Celsius. All patients will be covered by forced warm air blankets. For induction and maintenance of anesthesia, propofol combined with remifentanil and rocuronium will be used. Depth of anesthesia is aimed at a bispectral index of 50 +/- 5.

In case of a moderate neuromuscular block (GROUP 1), rocuronium 0.6 mg/kg ideal body weight (IBW) bolus will be given at induction. After that, spontaneous recovery is allowed to a TOF ratio of 1.0. After that, if time allows, a new bolus rocuronium is given to reach the target depth of NMB of TOF 1-3. No reversal agent will be given in this group unless deemed necessary by the attending anesthesiologist.

In case of a deep neuromuscular block (GROUP 2), rocuronium 1.0 mg/kg IBW will be given at induction, aimed at a PTC of 1-2. If necessary extra rocuronium is given to reach the target depth of NMB. When PTC is 1 or 2, spontaneous recovery is allowed to a PTC of 10. After that, if time allows, a new bolus rocuronium is given to reach a target depth of NMB of PTC 1-2. For reversal, 4 mg/kg IBW sugammadex will be given at a NMB depth of 1-2 PTC.

Extubation in both groups will be performed if EMG TOF ratio values are > 0.9

The attending anesthesiologist will be responsible for the anesthesia and safety of the patient at any time during the experiment. He or she may decide to discard the protocol if this is required for safety reasons. Measurements will be performed and recorded in the CRF by a separate researcher in the operating theater.

In case of suboptimal surgical conditions, extra muscle relaxants may be given at any time as needed.

5.1.2 Neuromuscular monitoring

During this study we will use two or three devices to monitor neuromuscular block. The TOF cuff and EMG will be applied on the same arm. See next paragraphs for detailed explanation.

Application of the TOF cuff

The TOF cuff (*RGB medical devices, Spain*) blood pressure cuff will be applied on a upper arm (50 dominant and 50 non dominant arm) according to the manufacturers guidelines.

The electrodes in the TOF cuff blood pressure cuff are placed on the medial aspect of the upper arm in the arm nerve pathway. See fig 3.

[figure not shown]

Fig 3. TOF cuff (from rodiera et al (6))

Application of electromyography

A Neuromuscular Transmission module (E-EMT-01) with the Carescape B450 monitor (both *GE Healthcare, Finland*) will be used for EMG measurements. Electrodes will be applied after degreasing the skin with alcohol and shaved if necessary to reduce impedance. Studies have demonstrated that EMG TOF ratio measured at the first dorsal interosseous muscle is equivalent to MMG during the late phase of recovery (TOF ratio > 0.70). Hence, EMG at the first dorsal interosseous is an alternative gold standard for detecting residual neuromuscular block in clinical settings. Additionally, EMG yields more consistent responses because it is not affected by restriction of movement of the muscle and is devoid of the staircase phenomenon. The stimulating negative electrode (brown) will be positioned 1 cm proximal to the wrist skin crease over the ulnar nerve and the positive electrode (white) 3 to 5 cm proximal. The black earth electrode will be placed at the proximal wrist crease. The green sensing electrode will over the FDI muscle and the red electrode at the insertion of the muscle (see Fig 3. (9))

In the 50 additional patients where the AMG is not applied, the EMG will be applied on both arms following the procedure stated above.

Fig 3. Application of the EMG on the first dorsal interosseous (from Phillips et al.(9))

Calibration

After induction, but before administration of the muscle relaxant rocuronium, all neuromuscular monitoring devices will be calibrated according to the manufacturers guidelines and good clinical research practice guidelines in pharmacodynamic studies of neuromuscular blocking agents to ensure supra maximal stimulation.(3) Supra maximal stimulation is the maximal stimulation current (eg. a greater stimulus does not result in a greater response) with an added 20%. All devices have an inbuilt calibration program to detect the maximal stimulation current. Pulse width in all devices is set at 200 microseconds (default). After calibration, 3 consecutive measurements will be performed to ensure precise measurements. In case of >5% difference between measurements, the device will be recalibrated.

5.2 Withdrawal of individual subjects

Subjects can decide to leave the study at any time, for any reason if they wish to do so, without any consequences. The responsible investigator can also decide to exclude a subject if by continuing participation the subjects' wellbeing is harmed in any way. Subjects can also be excluded in case of protocol violations and noncompliance.

In case of dropping out from the study at the subject's own request, the subject is asked permission for using the data already collected. The subject is allowed to decline this request, without giving any reason, and again without any consequences. When permission is not granted to use already available data, this specific data is deleted from the database and any paperwork will be disposed of.

In case of withdrawal the subject will be replaced by another patient.

6. STUDY MEASUREMENTS

General

- Patient characteristics including age, gender, weight, height, BMI, ASA class, underlying disease, medication, comorbidity.
- Duration of surgery and anesthesia;
- Drug dosages and administration times (propofol, opioid, muscle relaxant, reversal agent, other agents used during anesthesia);
- Temperature (central and periferal)
- Time of extubation

Neuromuscular data

Group 1

- Onset:
 - T1 90% depression time will be recorded after administration of rocuronium for all devices
- Recovery:
 - Time to reappearance of T1, T2, T3 and T4
 - Time to T1=25%
 - Time to TOF ratio 0.9
 - Continuous comparisons between the devices at 30 seconds intervals (as outlined before) until TOF ratio 1.0

Group 2

- Onset:
 - T1 90% depression time will be recorded after administration of rocuronium for all devices
- Recovery:
 - Continuous comparisons between the devices at 5 minutes intervals (as outlined before) between PTC 1-10
 - Continuous comparisons between the devices at 30 seconds intervals (as outlined before) until TOF ratio 1.0 after reversal.

7. Statistics

Recovery of neuromuscular block will be compared by the Bland–Altman analysis for repeated measurements for TOF cuff vs. EMG (See Olofson et al.(10)). This analysis allows estimation of agreement between the devices by estimating bias (D) and the 95% limits of agreement (L). Small bias and narrow limits of agreement indicate strong agreement. Additionally, this analysis accounts for the effect of instrumental imprecision by evaluating the repeatability coefficient of each device. A small repeatability coefficient indicates high precision of the device. The limits of agreement capture 95% of differences between the compared devices. We defined clinically acceptable agreement as a bias <0.025 and limits of agreement within -0.050 to 0.050 .

The protocol was amended (19-11-2018) to include 50 extra patients to investigate relative bias between ipsi- and contralateral comparisons between TOF Cuff and EMG in patients with normal BMI. Bias of ipsi- and contralateral comparisons of TOF Cuff vs. EMG will be compared. A relative bias of <5% is defined acceptable.

Regarding precision, a one-way analysis of variance will be performed on the sets of consecutive TOF ratios measured by the same device during steady-state NMB maintenance conditions. The 95% repeatability coefficient (r) is defined as 1.96 times the standard deviation of the differences between 2 consecutive measurements.

Additionally we will construct Receiver Operating Curves (ROC) to assess the specificity and sensitivity of the TOF cuff versus EMG (gold standard) at various levels of NMB depth.

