7.1 Sample size

Previous results of Rodiera et al. yielded a bias (D) of -0.02 and limits of agreement (L) of -0.035 to -0.012 for the comparison of TOF cuff vs EMG at a TOF ratio of 0.7 and D 0.05 and L 0.04 – 0.06 at TOF 0.1.(6) We are not informed about D and L during deeper levels of neuromuscular block, and at TOF ratio 0.9 which is a clinically important level for safe extubation of a patient. Furthermore, precision was not assessed in this study and no comparisons were made with AMG and EMG.

We will therefore perform a pilot study with 200 patients (100 patients with normal BMI ($< 30 \text{ kg/m}^2$) and 100 patients with morbid obesity ($>30 \text{ kg/m}^2$)) to ensure that reliable estimates of repeatability coefficient (r), bias (D), and limits of agreement (L) are obtained. After 100 patients (50 non-obese/50 obese) we will perform an interim analysis and calculate the remaining number of patients needed to complete the study.

The protocol was amended (19-11-2018) to include 50 extra patients to investigate relative bias between ipsi- and contralateral comparisons between TOF Cuff and EMG in patients with normal BMI. The total number of included patients will be 250. A sub analysis of the first 20 patients shows that it takes 30 (SD 18.0) minutes until spontaneous recovery to a Tof Ratio of 0.9 is achieved. The EMG group required 47 minutes. To exclude possible outliers in our previous study we expect a mean time to a Ratio 0.9 of 42 minutes. With an α of 0.05 and β of 0.9 we require 24 patients. In the same sub analysis we saw that approximately half of the patients require additional muscle relaxants,

meaning that complete recovery is not achieved in half of the cases. In order to acquire a proper sample size to compare recovery to a Tof Ratio of 0.9 we will need a total of 50 patients to assess neuromuscular recovery on both ipsi- and contralateral extremities with the Tof Cuff.

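### One agreement rule covers the whole recovery with no TOF ratio level attached, so it mixes biases that may differ in sign and gives no bias or limits at TOF ratio 0.9

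*Combined protocol and SAP*

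**What the plan says.** Section 7 (Statistics) compares the TOF cuff with EMG during recovery by a Bland-Altman analysis for repeated measurements. It describes the limits of agreement as containing 95% of the between-device differences, adds that "Small bias and narrow limits of agreement indicate strong agreement", and then sets the rule: "We defined clinically acceptable agreement as a bias <0.025 and limits of agreement within -0.050 to 0.050". It names no TOF ratio level or range for that rule, and does not say whether levels are combined or judged separately.

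Under Section 6 (Study measurements), paired readings run up to TOF ratio 1.0 in group 1. In group 2 they are "Continuous comparisons between the devices at 30 seconds intervals (as outlined before) until TOF ratio 1.0 after reversal".

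Section 7.1 (Sample size) gives the prior evidence by level. At TOF ratio 0.7 an earlier study "yielded a bias (D) of -0.02 and limits of agreement (L) of -0.035 to -0.012"; the other result is "D 0.05 and L 0.04 – 0.06 at TOF 0.1". It continues: "We are not informed about D and L during deeper levels of neuromuscular block, and at TOF ratio 0.9", and calls 0.9 clinically important for safe extubation. For that reason the study is planned "to ensure that reliable estimates of repeatability coefficient (r), bias (D), and limits of agreement (L) are obtained".

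**The concern.** Section 7.1 treats agreement as something that changes with the level of block, and names 0.9 as the level where knowledge is missing. Section 7 does not carry this into the analysis or the rule. The natural reading, though not a stated one, is a single combined verdict.

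If bias changes sign along recovery, a combined bias can look small because opposite errors cancel. The combined limits then depend on how many pairs fall at each level. The design does not fix that mix: it depends on how long patients spend at each level, on group 2 readings after reversal, and on how many recover fully (about half did not in the sub-analysis of the first 20 patients, Section 7.1). Neither combined figure says how the cuff performs at 0.9.

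A smaller matter is that the bias criterion has no absolute value, so taken literally it bounds bias on the positive side only.

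**Working it through.** **Plan's own figure.** The plan gives no calculation for the agreement rule. Its one computed sample size, 24, concerns time to TOF ratio 0.9. It reproduces as (18 × (1.960 + 1.282) / (42 - 30))² = 23.6, rounded up to 24, and does not use the rule.

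**Step 1: the rule at each prior level (Section 7.1, values as printed).**

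| TOF ratio | Bias | Limits | Result |
|---|---|---|---|
| 0.7 | -0.02 | -0.035 to -0.012 | passes |
| 0.1 | +0.05 | 0.04 to 0.06 | fails on bias and upper limit |

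**Step 2: combining the two levels.** Assume the printed limits are 95% limits, with half-widths 0.0115 at 0.7 and 0.010 at 0.1. Let w be the share of pairs at 0.1.

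- Bias D = 0.05w - 0.02(1 - w). This is zero at w = 0.02/0.07 = 0.286, although neither level has zero bias.
- Within-level variance = w(0.010/1.96)² + (1 - w)(0.0115/1.96)².
- Between-level variance = w(1 - w) × 0.07².
- Limits = D ± 1.96 × √(within + between).

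| w | D | Limits | Result |
|---|---|---|---|
| 0.03 | -0.018 | -0.044 to 0.008 | passes |
| 0.058 | -0.016 | -0.050 to 0.018 | boundary |
| 0.10 | -0.013 | -0.056 to 0.030 | fails |
| 0.50 | 0.015 | -0.054 to 0.084 | fails |
| 0.90 | 0.043 | 0.001 to 0.085 | fails |

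The boundary is 5.8%. It is 3.6% if the bias at 0.7 is taken as the midpoint of its limits, (-0.035 - 0.012)/2 = -0.0235, and 5.1% or 6.4% if the half-width at 0.7 is 0.015 or 0.008. Hence about 4-6%. It also depends on the bias assumed at the higher level: with zero bias there and the same half-width, the same formulas (0.05² replacing 0.07²) give about 19%.

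**Step 3: the missing absolute value.** With limits of half-width h, a negative bias meets the rule as written down to -(0.050 - h). For h = 0.010 that is -0.040; for h = 0.0115 it is -0.0385. Once h reaches 0.025 nothing beyond -0.025 can pass. The gap therefore covers biases between -0.025 and -0.050, and only with half-widths below 0.025.

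**Step 4: precision of a level-specific limit.** Assume one difference per patient and true limits of ±0.05, so SD = 0.05/1.96 = 0.0255. The 95% half-width is 1.96 × SD × √(1/n + 1.96²/(2(n - 1))): 0.005 at n = 250, 0.008 at n = 125, 0.012 at n = 50 and 0.017 at n = 25.

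**The case against.** **The plan does look at the extubation range.** Section 7 plans ROC curves at several depths of block, Section 6 records time to TOF ratio 0.9 in group 1, and an amendment moves 50 patients to the LUMC to capture late spontaneous recovery. That is true, and a reader should not infer that 0.9 is ignored. But a ROC curve gives sensitivity and specificity, and a time is in minutes. Neither yields the bias and limits that Section 7.1 says are unknown.

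**A combined rule is strict, not lenient.** This largely stands. A reader might infer that the same data could pass or fail depending on whether between-level spread enters the limits. Section 7 does not support that, because it says the limits contain 95% of differences. At w = 0.50, limits from within-level variance alone would be 0.004 to 0.026. These lie between the two groups of differences and contain almost none of them. With the spread included, a combined pass is confined to a small share of pairs at 0.1.

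**The prior figures are weak.** This also stands. The Introduction describes the earlier comparator as mechanomyography, while Section 7.1 labels the figures as against EMG and then says that no comparison with EMG was made. The limits at 0.7 are not centred on the bias. Two points stand in for a continuous recovery. The gap in Section 7 does not depend on these figures; the size of the illustration does.

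**The absolute value is only wording.** Agreed. The symmetric limits and the phrase about small bias suggest that magnitude was meant.

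**Should deep-block counts be excluded?** Group 2 also has "Continuous comparisons between the devices at 5 minutes intervals (as outlined before) between PTC 1-10", and a reader might infer that the rule should be confined to TOF ratios. The documents do not settle this, and confining it would leave deep block without a criterion, so it is not proposed here.

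**Conclusion.** The point holds as a cheap improvement. Followed as a single combined analysis, the plan would average biases that its own evidence puts on opposite sides of zero. With those figures it would fail the rule once more than about 4-6% of pairs lie at 0.1, even though 0.7 passes alone. It would also return no bias or limits at 0.9.

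The percentage rests on the printed limits being 95% limits, on two levels only, and on the bias at 0.7 representing higher levels. It illustrates the mechanism and does not predict this trial's result. A reader might go further and conclude that the device would be wrongly accepted at the extubation level. The documents give no bias at 0.9, so neither the direction nor the size of an error there can be stated.

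The missing absolute value is a real but minor flaw in a decision threshold.

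**What to change.** In Section 7:

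- Model the cuff-minus-EMG TOF-ratio difference against TOF ratio level with a patient random effect, or use an equivalent level-specific Bland-Altman analysis.
- Report bias and limits with 95% confidence intervals at prespecified levels, including 0.9.
- State the level or levels at which the acceptance rule is judged.
- Write the bias criterion as |bias| <0.025.

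No new data are needed; the cost is SAP wording and modest extra code. The downside is precision. Under the assumptions of Step 4, the 95% interval around a limit is about ±0.005 if all 250 patients contribute at a level, ±0.008 if 125 do, and ±0.017 if 25 do (half of the 50-patient extension). Repeated pairs per patient would change these figures. Against a margin of ±0.050, the smaller subsets would give only a rough answer, and the report should say so.
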